12.5 Interim Analysis

We will perform an interim analysis at one month from the initiation of the study

12.6 Reporting and Exclusions

12.6.1 Evaluation of Toxicity

All subjects will be evaluable for toxicity from the time of their first treatment in either treatment arm. Two-sided exact Clopper-Pearson 95% confidence intervals will be calculated for all toxicity proportions to assess the precision of the obtained estimates.

12.6.2 Evaluation of Response

All subjects included in the study will be assessed for response to treatment according to the intention to treat (ITT).

13. Adverse Event Reporting Requirements

Adverse event (AE) monitoring and reporting is a routine part of every clinical trial. The investigator will be required to provide appropriate information concerning any findings that suggest significant hazards, contraindications, side effects, or precautions pertinent to the safe use of the drug or device under investigation. Safety will be monitored by evaluation of adverse events reported by subjects or observed by investigators or research staff, as well as by other investigations such as clinical laboratory tests, x-rays, computed tomography (CT), electrocardiographs, etc.

13.1 Adverse Event Definition

An adverse event (also referred to as an adverse experience) can be any unfavorable and unintended sign (e.g., an abnormal laboratory finding), symptom, or disease temporally associated with the use of a drug, and does not imply any judgment about causality. An adverse event can arise with any use of the drug (e.g., off-label use, use in combination with another drug) and with any route of administration, formulation, or dose, including an overdose.

Because this is a trial focusing on a critically ill population where adverse events are expected to occur frequently, only AEs meeting the following criteria will be collected and reported:

1. AEs related to bleeding (any major or clinically significant non-major bleeding) or thrombotic events (DVT/PE, stroke, myocardial infarction, peripheral embolism, skin thrombosis).
2. Any adverse event that results in interruption or discontinuation of the assigned anticoagulant treatment.
3. Any adverse event that meets the criteria for serious, as defined in Section 13.2.

13.1.1 Investigational Agent or Device Risks (Expected Adverse Events)

Expected adverse events for drugs administered as part of this protocol may be found in

the package inserts, located in Appendix A.

13.1.2 Adverse Event Characteristics and Related Attributions

CTCAE term (AE description) and grade: The descriptions and grading scales found in the revised NCI Common Terminology Criteria for Adverse Events (CTCAE) version 5.0 will be utilized for AE reporting. A copy of the CTCAE version 5.0 can be downloaded from the CTEP web site (<http://ctep.cancer.gov>).

- **Attribution** of the AE:

- Definite – The AE *is clearly related* to the study treatment.
- Probable – The AE *is likely related* to the study treatment.
- Possible – The AE *may be related* to the study treatment.
- Unlikely – The AE *is doubtfully related* to the study treatment.
- Unrelated – The AE *is clearly NOT related* to the study treatment.

13.1.3 Recording of Adverse Events

All adverse events described in section 13.1 will be recorded on a subject specific AE log. The AE log will be maintained by the research staff and kept in the subject's research chart.

13.1.4 Reporting of AE to WCM IRB

All AEs occurring on this study will be reported to the IRB according to the IRB policy, which can be accessed via the following link:
http://researchintegrity.weill.cornell.edu/forms_and_policies/forms/Immediate_Reportin
Policy.pdf.

13.1.5 Reporting Events to Participants

Participants will be informed of any adverse event related to the anticoagulant treatment that represents a new or increased risk from participating in the study.

13.1.6 Events of Special Interest

Not applicable.

13.1.7 Reporting of Pregnancy

Not applicable.

13.2 Definition of SAE

SAEs include death, life threatening adverse experiences, hospitalization or prolongation of hospitalization, disability or incapacitation, overdose, congenital anomalies and any other serious events that may jeopardize the subject or require medical or surgical intervention to prevent one of the outcomes listed in this definition.

13.2.1 Reporting of SAE to IRB

All SAEs occurring on this study will be reported to the IRB according to the IRB policy, which can be accessed via the following link:

http://researchintegrity.weill.cornell.edu/forms_and_policies/forms/Immediate_Reportin
Policy.pdf.

13.2.2 Reporting of SAE to FDA

IND application sponsor must report any suspected adverse reaction or adverse reaction to study treatment that is both serious and unexpected. Unexpected fatal or life-threatening suspected adverse reactions represent especially important safety information and must be reported to FDA as soon as possible but no later than 7 calendar days following the sponsor's initial receipt of the information.

- i. death,
- ii. a life-threatening adverse event,
- iii. in-patient hospitalization or prolongation of existing hospitalization,
- iv. a persistent or significant incapacity or substantial disruption of the ability to conduct normal life functions, or
- v. a congenital anomaly or birth defect

Important medical events that may not result in death, be life-threatening, or require hospitalization may be considered serious when, based upon appropriate medical judgment, they may jeopardize the patient or research subject and may require medical or surgical intervention to prevent one of the outcomes listed as serious

CDER INDs:

Food and Drug Administration
Center for Drug Evaluation and Research
Division of xxxx Products
[name]
[name]

13.3 AE/SAE Follow Up

All SAEs and AEs reported during this study will be followed until resolution or until the investigator confirms that the AE/SAE has stabilized and no more follow-up is required. This requirement indicates that follow-up may be required for some events after the subject discontinues participation from the study.

13.4 Time Period and Frequency for Event Assessment and Follow Up

The occurrence of an adverse event (AE) or serious adverse event (SAE) may come to the attention of study personnel during study visits and interviews of a study participant presenting for medical care, or upon review by a study monitor.

All AEs including local and systemic reactions not meeting the criteria for SAEs will be captured on the appropriate case report form (CRF). Information to be collected includes event description, time of onset, clinician's assessment of severity, relationship to study product (assessed only by those with the training and authority to make a diagnosis), and time of resolution/stabilization of the event. All AEs occurring while on study must be documented appropriately regardless of relationship. All AEs will be followed to adequate resolution.

Any medical condition that is present at the time that the participant is screened will be considered as baseline and not reported as an AE. However, if the study participant's condition deteriorates at any time during the study, it will be recorded as an AE.

Changes in the severity of an AE will be documented to allow an assessment of the duration of the event at each level of severity to be performed. AEs characterized as intermittent require documentation of onset and duration of each episode.

The study team will record all reportable events with start dates occurring any time after informed consent is obtained until 7 (for non-serious AEs) or 30 days (for SAEs) after the last day of study participation. At each study visit, the investigator will inquire about the occurrence of AE/SAEs since the last visit. Events will be followed for outcome information until resolution or stabilization.

14. Unanticipated Problems Involving Risks to Subjects or Others

14.1 Definition of Unanticipated Problems Involving Risks to Subjects or Others (UPIRTSO)

The Office for Human Research Protections (OHRP) considers unanticipated problems involving risks to participants or others to include, in general, any incident, experience, or outcome that meets all of the following criteria:

- Unexpected in terms of nature, severity, or frequency given (a) the research procedures that are described in the protocol-related documents, such as the Institutional Review Board (IRB)-approved research protocol and informed consent document; and (b) the characteristics of the participant population being studied;
- Related or possibly related to participation in the research ("possibly related" means there is a reasonable possibility that the incident, experience, or outcome may have been caused by the procedures involved in the research); and
- Suggests that the research places participants or others at a greater risk of harm (including physical, psychological, economic, or social harm) than was previously known or recognized.

14.1.2 Unanticipated Problem Reporting

The investigator will report unanticipated problems (UPIRTSOs) to the reviewing Institutional Review Board (IRB) and to the Data Coordinating Center (DCC)/lead principal investigator (PI). The UPIRTSO report will include the following information:

- Protocol identifying information: protocol title and number, PI's name, and the IRB project number;

- A detailed description of the event, incident, experience, or outcome;
- An explanation of the basis for determining that the event, incident, experience, or outcome represents an UPIRTSO;
- A description of any changes to the protocol or other corrective actions that have been taken or are proposed in response to the UPIRTSO.

To satisfy the requirement for prompt reporting, UPIRTSOs will be reported using the following timeline:

- UPIRTSOs that are serious adverse events (SAEs) will be reported to the IRB and to the DCC/study sponsor within <insert timeline in accordance with policy> of the investigator becoming aware of the event.
- Any other UPIRTSO will be reported to the IRB and to the DCC/study sponsor within <insert timeline in accordance with policy> of the investigator becoming aware of the problem.
- All UPs should be reported to appropriate institutional officials (as required by an institution's written reporting procedures), the supporting agency head (or designee), Food and Drug Administration (FDA), and the Office for Human Research Protections (OHRP) within <insert timeline in accordance with policy> of the IRB's receipt of the report of the problem from the investigator.

15. Data and Safety Monitoring Plan (DSMP)

The Weill Cornell Medical College Data Safety Monitoring Board (DSMB) is being requested to review safety data and to make recommendations regarding continuation, termination, or modification to the study.

During the study, the DSMB will regularly (every 6 months) review all incidences of symptomatic DVT and PE, clinically relevant bleeding, and death, including those not yet adjudicated, which will result in recommendations to the study team.

An interim analysis will be performed one month after the first patient is enrolled.

16. References

- 1- Tang N et al. Abnormal coagulation parameters are associated with poor prognosis in patients with novel coronavirus pneumonia. *J Thromb Haemost* 2020 epublished

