FDA	Food and Drug Administration
GCP	Good Clinical Practice
HIPAA	Health Insurance Portability and Accountability Act of 1996
HRBFA	Human Research Billing Analysis Form
HIT	Heparin-Induced Thrombocytopenia
HUD	Humanitarian Use Device
ICF	Informed Consent Form
ICU	Intensive Care Unit
IDE	Investigational Device Exemption
IND	Investigational New Drug
IRB	Institutional Review Board
ISTH	International Society of Thrombosis and Haemostasis
KDIGO	Kidney Disease Improving Global Outcomes
LDH	Lactate Dehydrogenase
LMWH	Low-Molecular-Weight Heparin
PHI	Protected Health Information
PI	Principal Investigator

PT	Prothrombin Time
REDCap	Research Electronic Data Capture
RNA	Ribonucleic Acid
RT-PCR	Reverse Transcriptase Polymerase Chain Reaction
SAE	Serious Adverse Event
SC	Subcutaneous
SGOT	Serum Glutamic Oxaloacetic Transaminase
SGPT	Serum Glutamic Pyruvic Transaminase
SUSAR	Suspected Unexpected Serious Adverse Reaction
UFH	Unfractionated Heparin
UIRTSO	Unanticipated Problem Involving Risks to Subjects or Others
VTE	Venous Thromboembolism
VWF	Von Willebrand Factor
WCM	Weill Cornell Medicine

1. Protocol Summary

Full Title:	InterMediate ProphylACTic versus Treatment Dose Anticoagulation in Critically Ill Patients with COVID-19: A Prospective Randomized Study (The IMPACT Trial)
Short Title:	The IMPACT Trial
Clinical Phase:	IV
Principal Investigator:	[name]., M.Sc.
Study Description:	
The purpose of this study is to determine if therapeutic dose anticoagulation (experimental group) improves 30-day mortality in participants with COVID-19 compared to those receiving the intermediate dose prophylaxis (control group). Following screening, subjects will be randomized 1:1 to intermediate dose prophylaxis or therapeutic anticoagulation treatment arms. Treatment will continue for 28 days with longer-term follow-up through 6 months.

Sample Size:	N=186; 93 patients per cohort
Enrollment:	The study will enroll 186 subjects and screen up to 300 subjects
Study Population:	Adult patients with documented COVID-19 infection
Enrollment Period:	6 months

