6.1.2 Treatment Phase

Eligible subjects will be randomly assigned to Intermediate Prophylaxis Dose or Therapeutic Anticoagulation treatment groups in a 1:1 ratio. Treatment will continue for 28 days continuously.

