12.2 Sample Size/Accrual Rate

N=93 subjects per treatment arm (186 total). With approximately 93 patients in each treatment arm, a two-sample chi-square test with a 0.05 two-sided significance level will have 80% power to detect a difference in the 30-day mortality proportion between treatment arms of 12 % or greater. This calculation assumes a 30-day mortality proportion of approximately 15 % in the intermediate dose prophylaxis arm.

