12.4 Analysis of Endpoints

12.4.1 Analysis of Primary Endpoints

The chi-square test will be used to compare the proportion of patients who die by 30 days between the two treatment arms. A two-sided 95% confidence interval for the difference in the 30-day mortality proportion between the two arms will be calculated to assess the precision of the obtained estimate. All other efficacy outcome proportions and safety outcome proportions will be compared between the two treatment arms by the chi-square test or Fisher's exact test, as appropriate. Two-sided exact Clopper-Pearson 95% confidence intervals will be calculated for treatment arm differences, as appropriate. Participants who are discharged prior to day 30 for whom vital status cannot be assessed will be censored from the analysis. We expect this to occur only rarely.

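### The 6-month DSMB review cycle equals the planned enrolment period, so on plan about 155 of 186 patients are randomised between month 1 and month 6 with no DSMB review scheduled in that interval

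*Combined protocol and SAP*

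**What the plan says.** Section 15 (Data and Safety Monitoring Plan) asks an institutional DSMB to look at safety data and "make recommendations regarding continuation, termination, or modification to the study". It sets the frequency: "During the study, the DSMB will regularly (every 6 months) review all incidences of symptomatic DVT and PE, clinically relevant bleeding, and death". It does not say when the 6-month clock starts.

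The Protocol Summary gives "Enrollment Period: 6 months" for 186 patients. Section 6.1.2 says "Treatment will continue for 28 days continuously", and Section 6.1.3 adds a 6-month follow-up phase.

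The only other scheduled look is an interim, which is anchored in two ways. Section 12.5: "We will perform an interim analysis at one month from the initiation of the study". Section 15: "An interim analysis will be performed one month after the first patient is enrolled". Neither place gives its content, purpose or recipient, although in Section 15 it directly follows the DSMB text.

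The primary analysis (Section 12.4.1) is to "compare the proportion of patients who die by 30 days between the two treatment arms". On the control rate, Section 12.2 says: "This calculation assumes a 30-day mortality proportion of approximately 15 % in the intermediate dose prophylaxis arm".

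**The concern.** The DSMB is the body that the plan asks to recommend stopping or changing the trial. Its review interval is as long as the whole enrolment period, while each patient is treated for 28 days. If the first 6-monthly review falls about when the last patient is randomised, an excess of bleeding or death in one arm could build up through most of the trial before a scheduled comparison by arm reaches the board. A recommendation at that point could change little of what patients in this trial receive.

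The one-month interim might seem to cover this. It comes when few patients are enrolled and few outcomes are known, and the plan does not say that the DSMB receives it.

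**Working it through.** **Inputs from the documents.** N = 186 and 6-month enrolment (Protocol Summary); DSMB interval 6 months and interim at month 1 (Section 15); 28 days of treatment (Section 6.1.2); control 30-day mortality about 15% and a 12-point difference (Section 12.2).

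**Assumptions.** Uniform accrual; a month of 365.25/12 = 30.44 days; the interim counted from first enrolment; the DSMB clock starting near first enrolment. None of these accrual or clock details is in the plan.

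**The plan's own figure.** The pooled chi-square formula for 15% v 3% at two-sided 0.05 and 80% power gives 89 per arm, and 93 per arm gives 82.1% power. A control rate of 15.5% with the same 12-point difference gives exactly 93, so rounding of the inputs explains it. The opposite direction, 15% v 27%, would need 180 per arm, so 15% v 3% is the plan's alternative. N = 186 is taken as given below.

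**On-plan gap.**
- Accrual: 186/6 = 31 per month.
- Randomised from month 1 to month 6: 186 − 31 = 155, and 155/186 = 83%.
- Expected deaths among them by their own Day 30: 155 × 0.15 = 23 if both arms are at 15%. At 9% on average, (15% + 3%)/2, it is 155 × 0.09 = 14.
- Within 28 days of randomisation at month 6: 31/30.44 × 28 = 28.5. Past Day 28: 186 − 28.5 = 157.5, about 85%. Still to randomise: 0.

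**How the gap moves with the assumptions.**

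| Scenario | Randomised between month 1 and first 6-monthly review |
|---|---|
| Uniform, 6 months, clock at first enrolment | 155 (83%) |
| Linear ramp-up over the first 1 / 2 / 3 months | 169 / 177 / 179 |
| First month 1.5 / 2 times as fast as the rest | 143 / 133 |
| Accrual takes 9 / 12 months | 103 / 78 (with 62 / 93 still to enrol at month 6) |
| First review at month 3 / 4 / 5 | 62 / 93 / 124 |

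If the interim does not go to the DSMB, all 186 are randomised on plan before the first DSMB review at month 6 (124 or 93 with 9- or 12-month accrual).

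**What the month-1 look contains, on plan.**
- Enrolled: 31.
- Expected with 30 full days of follow-up: 31/30.44 × 0.44 = 0.45.
- Deaths visible at 15%: 0.45 × 0.15 + 30.55 × 0.15 × 0.5 = 2.4 if death times are uniform over 30 days, or 2.9 if deaths come early (median day 10). At 9% these are multiplied by 0.6: 1.4 and 1.7.
- A death settles the endpoint at once, so determined outcomes at 15% are about 2.4 + 0.45 × 0.85 = 2.7.

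**Enrolment-linked reviews, for comparison.** Reviews after 31, 62, 93 and 140 patients fall at months 1, 2, 3 and 4.5 on plan. Visible deaths at the last three are about 7, 12 and 19 at 15%, or about 4, 7 and 11 at 9%. The longest stretch without a review is 140 − 93 = 47 patients (25%).

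**The case against.** A reader might infer that 155 patients are never reviewed by the DSMB. The documents do not support that. The 6-monthly review covers all listed events during the study, and follow-up runs 6 months after treatment, so these patients' events are reviewed, but late. Nor does the plan forbid an unscheduled DSMB meeting; it simply schedules none in that interval.

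A reader might also infer that the one-month look can only be a safety look, or that it is an efficacy test. Neither follows, because Sections 12.5 and 15 state no purpose. What can be said is that it holds too little information to judge efficacy.

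Other safeguards continue. Treatment can be delayed or stopped for bleeding (Sections 7.7.1 and 7.9) and patients withdrawn for adverse events (8.2). AEs and SAEs go to the IRB (13.1.4 and 13.2.1), new safety information goes promptly to the IRB (11.2.1), and unanticipated problems go to the IRB and the coordinating centre or lead investigator (14.1.2, where the deadlines are unfilled template fields). FDA reporting is described for an IND sponsor (13.2.2). The trial is open-label, so the arm is known for each event. All of this stands, but none of it is a scheduled comparison by arm.

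Two further objections stand in part. A review interval is a design choice, and many schedules would do. Extra reviews would also rest on few deaths: with 7 deaths among 31 per arm, a 6 v 1 split gives Fisher p = 0.10, and only 7 v 0 falls below 0.05. That argues for board judgement over a formal boundary. It does not argue for waiting until enrolment ends.

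**Conclusion.** The concern holds in a conditional form. The 6-month interval, followed as written, can bring the first 6-monthly DSMB review at the point where enrolment closes. The figure of 155 (83%) is one scenario. It requires the clock to start near first enrolment, uniform accrual to plan, and the one-month interim to go to the DSMB. It is smaller with slower accrual, an earlier clock or a fast first month. It is larger with a ramp-up, if study initiation (the Section 12.5 anchor) precedes first enrolment, or if the interim is not a DSMB look. Even the smallest value examined, 62 patients, is a third of the trial.

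With 9- or 12-month accrual a month-6 review could still act, because 62 or 93 patients would remain to be enrolled. This is a point that should be fixed, held with medium confidence, because the plan does not state the clock, the accrual pattern or the interim's recipient.

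**What to change.** 1. In Section 15, replace the 6-month-only cycle with enrolment-linked reviews by the existing DSMB of deaths, bleeding and thrombosis by arm. One example is after about 31, 62, 93 and 140 randomised patients, and at least every 6 months. The sponsor may choose other triggers, provided the reviews fall during enrolment.
2. In Sections 12.5 and 15, use one anchor for the one-month look and name the DSMB as its recipient. On plan it coincides with the 31-patient review and can be the same meeting.
3. State that every one of these looks, and not only the first, is a descriptive safety review with no efficacy test and no stopping for benefit. The final mortality test then stays at 0.05.

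The cost is wording in two sections and, on plan, about three more DSMB reports and meetings, using data already collected. No extra patients are needed. The added reviews rest on the small death counts shown in the working, so they depend on the board's judgement.

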Appendix A

Package insert for each of the drugs used in this protocol is available at the links below:

Lovenox® (Enoxaparin sodium):

https://www.accessdata.fda.gov/drugsatfda_docs/label/2009/020164s085lbl.pdf

Sodium heparin (unfractionated heparin):

https://www.accessdata.fda.gov/drugsatfda_docs/label/2017/017029s140lbl.pdf

Argatroban Injection: https://www.accessdata.fda.gov/drugsatfda_docs/label/2011/022485lbl.pdf

ARIXTRA® (fondaparinux sodium):

https://www.accessdata.fda.gov/drugsatfda_docs/label/2005/021345s010lbl.pdf

